8.1.3 Target Volumes

GTV:

The gross tumor volume (**GTV**) will include the primary tumor (**GTV primary**) as well as positive pelvic and para-aortic lymph nodes (**GTV node**). Note that there will be no **GTV primary** in patients who are being treated postoperatively. The GTVs may be contoured separately or as a single **GTV**.

CTV 45:

A clinical target volume (**CTV 45**) will be contoured on and CT scans and including the GTV primary, cervix, uterus, parametria. The mesorectum may be included in the CTV for patients with radiologic or clinical evidence of uterosacral involvement. A distal vaginal margin of 4cm on clinical or radiographic disease will be required. These **CTVs** may be contoured as a single volume. Either the CTV or a separate ITV must then include an additional margin for organ motion on the cervix and uterus, which will be 1-2cm in the anterior/posterior/superior directions, and 0.5 – 1 cm in the lateral and inferior directions.

The **CTV45** will include the common, internal iliac, external iliac, obturator, and presacral lymph nodes. The inguinal nodes will be included for all tumors involving the distal vagina and vulva. The para-aortic nodes will be included for patients with involved pelvic lymph nodes. The CTV 45 will be contoured to include a 7 mm margin around the pelvic vessels with the following modifications [6,31]: To encompass lymph nodes around the common iliac vessels, contours will be extended to the psoas muscle and vertebral body posterolaterally. Obturator nodes will be covered by extending the external iliac contour posteriorly to join the internal iliac volume. The presacral lymph nodes will be covered by contouring a 1cm wide margin anterior to S1 to S3. The CTV 45 will stop inferiorly at the level of the femoral head and superiorly at the diaphragm (approximately T12-L1). All critical normal tissues will be excluded from the CTV expansions, as well as anatomic barriers to spread (i.e. fascial planes and bone). The nodal CTV will also be expanded to accommodate all pelvic and PA nodes seen on the planning image. (See the RTOG GYN atlas for examples: <http://www.rtog.org/gynatlas/main.html>.)

PTV 45:

A **PTV 45** will be created by expanding the union of all CTVs by 5-7mm in all directions to account for daily set-up uncertainty. All patients will have verification of treatment setup with on-board kV imaging and cone beam CT at the start of treatment and on a weekly basis, or more frequently if required.

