
The **PTV 45** will be planned with the goal of 95% coverage to 45Gy in 25 fractions (1.8Gy/fraction).

For patients with evidence of parametrial extension (CTV/PTV 55):

The **CTV 55** will be defined as the parametrium extending from the pelvic sidewall to 2cm from the center of the cervical canal, or center of the cervix if canal is not visible. Anteriorly this volume will be limited by peritoneum and bladder, posteriorly by the peritoneum and rectum. Superiorly and inferiorly it will be bounded by the extent of the cervix or **GTV**.

The **PTV 55** will be created by expanding the **CTV 55** by 5 mm, excluding critical normal tissue. **PTV 55** may be modified in the following manner to achieve appropriate sparing of bowel: The small bowel contour will be expanded by 3mm, and subtracted from the **PTV 55** volume.

The **PTV 55** will be planned to receive a goal of 95% coverage to 55 Gy in 25 fractions (2.2Gy/fraction).

The cervix and uterus will be preferentially boosted with brachytherapy. If this is not achievable, a sequential IMRT boost may be performed.

CTV/PTV boost:

The **CTV boost** will be created by expanding the GTV node by 3mm to account for microscopic extracapsular extension, excluding critical normal tissues.

The **PTV boost** will be created by expanding the CTV nodal boost by 5 mm, excluding critical normal tissue. **PTV boost** may be modified in the following manner to achieve appropriate sparing of bowel: The small bowel contour will be expanded by 3mm, and subtracted from the **PTV boost** volume. In dose cohorts 2 and 3, the same will be applied to the large bowel contour (including sigmoid and rectum). These may be further modified to meet the strict criteria for normal tissue as outlined below.

The **PTV boost** will be the target of dose escalation in this trial and will receive 60 through 70Gy in 25 fractions (2.4 Gy/fraction – 2.8 Gy/fraction)

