8.1.6 Dose Limiting Toxicities (DLTs)

The National Cancer Institute’s Common Terminology Criteria for Adverse Events (CTCAE), version 4.0 will be used to score and grade treatment-related toxicity.

Two distinct toxicities are to be considered in this protocol: acute and late. These types of toxicity are distinct in terms of time of onset, character, management, and expected course, thus they will be considered separately for the purposes of determining the MTD.

Since integrated radiation dose escalation is unlikely to substantially affect the hematopoietic system, only non-hematologic, grade 3-4, acute toxicity will be considered the primary dose-limiting toxicity (acute DLT).

Acute DLT will be defined based on the side effects inherent from radiation therapy for gynecologic cancers, including effects on bowel, bladder, and skin. Dose limiting toxicity will include any of the following during treatment or within 6 weeks of completion:

1. Acute Grade 3-4 enteritis or proctitis requiring:
 - a. Tube feedings
 - b. Total parenteral nutrition
 - c. Hospitalization secondary to inadequate oral caloric or fluid intake
 - d. Prolonged treatment breaks secondary to enteritis (> 1 week)

e. Life-threatening consequences such as bowel perforation, obstruction, or bleeding requiring transfusion.

2. Acute Grade 3-4 bladder toxicity
 - a. Bladder ulceration or necrosis
 - b. Grade 3-4 cystitis including hematuria requiring transfusion
 - c. Urinary obstruction not due to clot passage
3. Grade 4 dermatologic toxicity (skin necrosis or ulceration of full thickness of dermis)

Late DLTs will be defined at grade 3-4 GI or GU toxicity with onset after 6 weeks of treatment. The CTCAE v 4.0 will be used for determination of late toxicity grade, with one exception: the use of plasma coagulation or similar procedure for rectal bleeding will not be considered a late DLT, even though it is considered a grade 4 toxicity by the CTCAE. If however, there are other consequences of radiation proctitis which meeting grade 3-5 criteria, this will be considered a late DLT.

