8.1.7 Dose Escalation Schema

Dose escalation will operate in the following fashion based on acute DLTs:

1. 3 patients will be accrued to dose level X (starting at level 1)
2. If there are any acute DLTs noted in these initial three participants, and additional three will be accrued (for a total of six).
3. If there is a second acute DLT, accrual will be halted for that cohort, and the dose will be deescalated to level X-1.
4. If 0/3 or 1/6 participants have an acute DLT, after a minimum follow up of 6 weeks, accrual to cohort X+1 may begin.
5. The candidate cohort for MTD will accrue a total of 6 patients. Thus if the dose deescalates, the dose cohort X-1 must have 6 participants before declaration of MTD. Similarly if the protocol proceeds to level 3, then it will accrue 6 participants even if no patient has an acute DLT.

The following schema will be used for late DLTs in conjunction with the above acute rules:

1. Patients will be monitored for late toxicity at every follow-up for 3 years.
2. If a late DLT observed in cohort Y, accrual in that and any higher cohort will be held until there is a minimum of 3 month follow up for all patients.
3. If a second late DLT is observed in cohort Y, then the dose will be de-escalated to Y-1 as per the above schema.
4. If there are no additional late DLTs in cohort Y, then a total of 6 patients must accrue to cohort Y, with a minimum of 3 months follow-up with no further late DLTs before the dose may be escalated to, or for accrual to resume in cohort Y+1.

Of note, acute and late DLTs will be counted separately. Thus if a patient has both an acute DLT and a late DLT, they will be counted as 1 DLT for both schema. If a patient has an acute DLT but not a late DLT, they will only be counted in the acute schema. The only exception will be a patient has an acute

DLT which does not resolve to less than grade 2 by 3 months: these will be counted as both acute and late toxicity for determination of MTD.

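### A first grade 4 skin necrosis more than 6 weeks after radiotherapy counts in neither DLT schema, a minor gap confined mainly to skin-adjacent primaries

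*Combined protocol and SAP*

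**What the plan says.** Section 8.1.6 sets the acute window: "Dose limiting toxicity will include any of the following during treatment or within 6 weeks of completion". Item 3 of the list that follows is the only skin item: "Grade 4 dermatologic toxicity (skin necrosis or ulceration of full thickness of dermis". The late definition is limited by organ: "Late DLTs will be defined at grade 3-4 GI or GU toxicity with onset after 6 weeks of treatment".

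Section 8.1.7 counts the two types separately. On the late side, "If a late DLT observed in cohort Y, accrual in that and any higher cohort will be held" until every patient has at least 3 months of follow-up, and a second late DLT de-escalates. Otherwise, "If there are no additional late DLTs in cohort Y, then a total of 6 patients must accrue to cohort Y", again with 3 months of follow-up, before escalation. The one bridge between the schemas is for an acute "DLT which does not resolve to less than grade 2 by 3 months: these will be counted as both acute and late toxicity".

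The escalated volume is nodal: under 8.1.3 the CTV boost "will be created by expanding the GTV node by 3mm to account for microscopic extracapsular extension". Of the groin, the same section says "The inguinal nodes will be included for all tumors involving the distal vagina and vulva", but this is in the description of CTV 45, which is planned at 1.8 Gy per fraction. Where brachytherapy of the primary is not achievable, 8.3 permits external-beam boosting to a total of 55-80 Gy, at either the level's fraction size or 1.8-2.0 Gy. Section 4.3 includes locally advanced vulvar cancer. Section 11 tabulates all toxicities by cohort, type and grade, and places the early/late cut at 4 weeks of treatment.

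**The concern.** The protocol treats full-thickness skin loss as severe enough to limit dose, then stops counting it on a calendar date. The bridging exception shows that skin damage which persists is accepted as late dose-limiting toxicity, provided it began early enough. An event of the same grade and cause that begins a little later contributes nothing.

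The primary objective is the maximum tolerated dose. An uncounted event would let the next level open, or the MTD be declared, with no prespecified response. Other safeguards are thin: 8.1.4 has no skin dose constraint, the serious-event table in 9.3 covers 30 days after the last treatment, and the tabulation in section 11 triggers no action. What remains is investigator judgement, which is not a rule for the MTD.

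**Working it through.** **1. The plan's own figure.** The maximum sample size in section 11 reproduces: 6 patients × 4 dose cohorts = 24. Adding an event type to a DLT definition does not alter it.

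**2. How the text scores events** (weeks counted from completion of radiotherapy):

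| Event | Acute schema | Late schema |
|---|---|---|
| Grade 4 skin, onset week 5, below grade 2 by 3 months | 1 | 0 |
| Grade 4 skin, onset week 5, not below grade 2 by 3 months | 1 | 1 |
| Grade 4 skin, first onset week 7 | 0 | 0 |
| Grade 3 GI or GU, first onset week 7 | 0 | 1 |

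The third row is the gap. The 6 weeks in the late definition are loosely worded, but neither reading brings skin in. Section 11's 4-week cut, taken literally, would shorten the skin window further.

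**3. Timing.** Section 11 expects about 4 patients per year: 52/4 = 13 weeks between patients, assuming steady accrual. Treatment lasts 25/5 = 5 weeks, so each patient clears the acute window at 5 + 6 = 11 weeks, before the next enters. When the last patient clears it, follow-up beyond the window is:
- 3 patients: 0 + 13 + 26 = 39 patient-weeks
- 6 patients: 0 + 13 + 26 + 39 + 52 + 65 = 195 patient-weeks

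**4. Assumed risk.** The documents give neither the share of exposed patients nor a late skin rate. Assume a per-patient probability p of first late-onset grade 4 skin toxicity from 0.05 × 0.02 = 0.001 (5% exposed, 2% risk) to 0.20 × 0.05 = 0.01 (20% exposed, 5% risk).

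**5. Chance of at least one uncounted event before the escalation decision.** P = 1 − ∏(1 − p·min(t, W)/W), where t is each patient's weeks past the window and W is the period over which events are spread evenly. W = 150 covers weeks 6 to 156 (the 3 years of late monitoring in 8.1.7). W = 26 puts all events early.

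| Cohort | W | p = 0.001 | p = 0.01 |
|---|---|---|---|
| 3 patients | 150 | 0.03% | 0.26% |
| 6 patients | 150 | 0.13% | 1.3% |
| 3 patients | 26 | 0.15% | 1.5% |
| 6 patients | 26 | 0.45% | 4.4% |

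For example, with 6 patients, W = 26 and p = 0.01: 1 − 0.995 × 0.99⁴ = 4.4%.

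**6. Missed de-escalation.** Two or more events in a cohort of 6 at p = 0.01: 0.006% (W = 150) or 0.079% (W = 26).

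**7. Upper bound over full follow-up.** Late DLTs can hold accrual after an escalation too. With 3 + 3 + 6 = 12 patients followed throughout, 1 − (1 − p)¹² = 1.2% to 11.4%. This overstates the effect, because some events would fall after the last decision. Two events in one cohort of 6 remain at about 0.15% at most.

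**The case against.** The strongest reply is that the gap lies largely outside what the trial escalates. The boost volume comes from pelvic and para-aortic nodes, and the groin is named only in the 1.8 Gy volume. A relevant event therefore needs a skin-adjacent primary, brachytherapy not achievable, and a physician who chooses the larger fraction over 1.8-2.0 Gy. This stands, and it is why the point is minor.

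A reader might infer that escalation raises the skin dose by 30% to 52%, since 25 fractions at the level's fraction give 60 to 70 Gy against 46 Gy in the vulvar series of 4.3 (60/46 = 1.30; 70/46 = 1.52). The documents do not support that. Section 8.3 allows 55-80 Gy to the primary at standard fractionation whatever the level, so escalation adds only an optional larger fraction. The comparator is also a neoadjuvant dose given before surgery. Its 50-60% rate is for acute grade 3-4 skin toxicity, whose grade 4 part is already counted if seen in the acute window.

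It can also be said that the different organ lists are deliberate. Section 8.1.6 says acute and late toxicities differ in nature and are considered separately, and 4.7 builds the late expectation on bowel, rectum and bladder. That explains why those organs are listed. It does not explain why skin is dropped, given the bridging exception.

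Finally, a wider definition invites wrong holds. Section 4.3 reports surgical wound complications in 20-30% of vulvar patients. With the assumed 5-20% exposed, 0.05 × 0.20 = 1% to 0.20 × 0.30 = 6% of patients might need adjudication, or 10 to 6 times the assumed true rate of 0.1% to 1%. This is an upper bound, since not all have surgery or reach grade 4, but the attribution burden is real.

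**Conclusion.** The gap is real on the text, and no other section closes it. Its practical weight is small: mainly a missed accrual hold, very rarely a missed de-escalation. The probabilities rest on assumed exposure and risk and on steady accrual; only the accrual rate and the time windows come from the protocol.

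Two further inferences go too far. One is that late skin events would be common in a cohort: if all 6 patients carried a 10% risk, at least one event would have a 47% chance (1 − 0.9⁶). Nothing in the documents puts all 6 at risk, and the narrow route through 8.3 argues against it. The other is that such events would go unrecorded. Toxicity is graded at follow-up and tabulated under section 11; what is missing is a rule that acts on it.

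This is a minor but cheap improvement to the safety and MTD rules.

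**What to change.** In 8.1.6, define a late DLT as grade 3-4 GI or GU toxicity, or grade 4 dermatologic toxicity by the criterion already used in the acute list, in the irradiated field, attributed to radiation and not to a surgical wound complication, with onset more than 6 weeks after completion of radiation. Keep the existing exception for plasma coagulation. Replace the 4-week cut in section 11 with the same 6-week cut, so that the two sections classify an event alike. The rules in 8.1.7 and the maximum of 24 stay as they are, and no visits are added.

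There are two costs. Someone must judge radiation necrosis against wound breakdown in vulvar patients who have surgery, and may sometimes be wrong; in the IMRT series of 4.3, wound complications took 3-6 months to heal. And a hold is slow: growing a cohort from 3 to 6 takes 3 × 13 = 39 weeks, plus one or two 13-week waits, so 52 to 65 weeks. Under the assumptions above, a true additional hold before escalating from 3 patients has a chance of 0.03% to 1.5%, and it would follow an event for which a pause is appropriate.

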8.1.7 Dose Escalation Schema

Dose escalation will operate in the following fashion based on acute DLTs:

1. 3 patients will be accrued to dose level X (starting at level 1)
2. If there are any acute DLTs noted in these initial three participants, and additional three will be accrued (for a total of six).
3. If there is a second acute DLT, accrual will be halted for that cohort, and the dose will be deescalated to level X-1.
4. If 0/3 or 1/6 participants have an acute DLT, after a minimum follow up of 6 weeks, accrual to cohort X+1 may begin.
5. The candidate cohort for MTD will accrue a total of 6 patients. Thus if the dose deescalates, the dose cohort X-1 must have 6 participants before declaration of MTD. Similarly if the protocol proceeds to level 3, then it will accrue 6 participants even if no patient has an acute DLT.

The following schema will be used for late DLTs in conjunction with the above acute rules:

1. Patients will be monitored for late toxicity at every follow-up for 3 years.
2. If a late DLT observed in cohort Y, accrual in that and any higher cohort will be held until there is a minimum of 3 month follow up for all patients.
3. If a second late DLT is observed in cohort Y, then the dose will be de-escalated to Y-1 as per the above schema.
4. If there are no additional late DLTs in cohort Y, then a total of 6 patients must accrue to cohort Y, with a minimum of 3 months follow-up with no further late DLTs before the dose may be escalated to, or for accrual to resume in cohort Y+1.

Of note, acute and late DLTs will be counted separately. Thus if a patient has both an acute DLT and a late DLT, they will be counted as 1 DLT for both schema. If a patient has an acute DLT but not a late DLT, they will only be counted in the acute schema. The only exception will be a patient has an acute

DLT which does not resolve to less than grade 2 by 3 months: these will be counted as both acute and late toxicity for determination of MTD.

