1.0 STUDY SYNOPSIS

This study involves administration of an integrated radiotherapy boost to cancerous unresected pelvic and para-aortic nodal disease from gynecologic cancers. Many studies have utilized a sequential boost to deliver a total dose of 55 – 60 Gy to the pelvic sidewall (covering the lower pelvic lymph nodes), including 8-10 Gy that is usually delivered with brachytherapy [3,9,32]. This study treatment plan will escalate the dose to pelvic and para-aortic nodal disease from 60 Gy in 2.4 Gy per fraction to 70Gy in 2.8 Gy per fraction in 3 dose cohorts, using an integrated boost technique utilizing the same number of fractions for all cohorts (25 fractions) while the elective volumes are held constant at 45Gy . The cervix and uterus will be preferentially boosted with brachytherapy if clinically indicated.

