2.0 HYPOTHESIS

Using a simultaneous integrated boost, the dose to treat involved para-aortic and pelvic lymph nodes can be safely escalated from 60 Gy in 2.4 Gy per fraction to 70 Gy in 2.8 Gy per fraction for a constant 25 total fractions.

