3.0 OBJECTIVES

3.1 Primary Objective

3.1.1 To determine the feasibility and maximum tolerated dose of integrated boost radiation therapy, administered with IMRT technique with concurrent chemotherapy (cisplatin).

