4.6 Reported toxicity in cervical cancer trials

The standard of care for FIGO stage IB2-IV cervical cancer is concurrent cisplatin and whole-pelvis radiation therapy, followed by brachytherapy [7,16,17,21,25,29]. The addition of chemotherapy improves overall and disease-free survival. With this standard treatment, reported rates of severe (grade 3-4) acute GI toxicity range from 7-25%, GU toxicity from 1-3%, and hematologic toxicity from 5-37% (Table 2). Severe (grade 3-4) late GI toxicity ranges from 3-12% and late GU from 2-17%. The wide range in incidence of toxicity may relate to the use of different grading scales between studies, use of crude toxicity estimates, and variation in quality of patient follow-up. Additionally, treatment varied between trials, with some employing a parametrial radiation boost [17,29] or adjuvant hysterectomy [16], in addition to whole pelvis chemoradiation and brachytherapy.

Depending on the technique, treating the para-aortic nodes and the whole pelvis with concurrent cisplatin, increases rates of acute and late GI toxicity [3,9,32]. In two prospective trials, GOG 125 and RTOG 92-10, patients were treated with concurrent EFRT, 5-FU and cisplatin [9,32]. In both trials, patients received brachytherapy and a parametrial boost to a total dose of 55-65 Gy. In GOG 125, reported grade 3-4 acute (19%) and late GI toxicity rates (14%) were similar to trials treating the whole pelvis with chemoradiation [32] (Table 2). Meanwhile, acute and late GI toxicity rates were much higher in RTOG 92-10 (50% and 34%, respectively), which likely relates to the fact that fractions of radiation were delivered twice daily and para-aortic nodal disease was boosted to total doses of 54 – 58 Gy with 3D conformal technique [9]. At the University of Pittsburg women were treated with concurrent cisplatin and intensity-modulated EFRT, including an IMRT boost to involved lymph nodes to 55-60Gy and a conventional (3D) parametrial boost to 50-60Gy [3]. Two-year toxicity rates were acceptable at 3% and 10% for grade 3-4 acute and late GI toxicity, respectively. Although a follow-up time of two years is short when assessing late toxicity, IMRT holds promise as a technique to deliver EFRT and boost nodal disease with potentially acceptable toxicity.

Table 2- Incidence of Grade 3 or 4 Toxicity with Concurrent Radiation Therapy and Chemotherapy

Study	n	Concurrent chemotherapy	Acute Hemato.	Acute GU	Acute GI	Late GU (year f/u)	Late GI (year f/u)

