6.0 PATIENT SELECTION

6.1 Conditions for Patient Eligibility

1. Biopsy confirmed . malignancy of the gynecologic tract.
2. Involved pelvic or para-aortic lymph nodes by imaging or pathology.
3. Treatment plan to include delivery of concurrent chemoradiotherapy .
4. Zubrod/ECOG performance status 0-2
5. ≥ 18 years of age.
6. Negative pregnancy test in women of child-bearing potential
7. ANC >1000 , Hgb >8.0 g/dl, Platelets $>80,000$ within 30 days of study entry
8. Creatinine <1.5
9. Signed study-specific informed consent.

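### One MTD is set for pelvic and para-aortic nodal boosts, but the escalation rules and toxicity tables ignore boost site, so it can be declared for both with few or no para-aortic boosts given

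*Combined protocol and SAP*

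**What the plan says.** The claim is made for both nodal sites. The hypothesis (section 2.0) is that "the dose to treat involved para-aortic and pelvic lymph nodes can be safely escalated from 60 Gy" to 70 Gy, and the synopsis (section 1.0) says "This study treatment plan will escalate the dose to pelvic and para-aortic nodal disease from 60 Gy in 2.4 Gy per fraction". The primary objective (section 3.1) is a single one: "To determine the feasibility and maximum tolerated dose of integrated boost radiation therapy".

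Entry needs only one of the sites. The second criterion in section 6.1 reads "Involved pelvic or para-aortic lymph nodes by imaging or pathology".

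The escalated volume pools them. In section 8.1.3 the gross tumor volume covers the primary tumor "as well as positive pelvic and para-aortic lymph nodes", and one boost volume is built from the nodal part. Section 8.1.5 gives one dose ladder for that volume.

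The decision rules in section 8.1.7 count patients only. A level clears with 0/3 or 1/6 acute DLTs, late DLTs have a parallel count, and "The candidate cohort for MTD will accrue a total of 6 patients". Section 11 breaks toxicity down by dose cohort, type, grade and early or late onset. No section sets a number of para-aortic boosts, stratifies by site, or limits the MTD to the sites treated.

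**The concern.** The rules would accept three, or six, patients boosted only in the pelvis. The level would then be cleared, or the MTD fixed, with no observation of an escalated dose to para-aortic nodes, yet the result would answer a hypothesis that names them. Because Section 11 does not split toxicity by site, a reader of the planned tables could not tell how many para-aortic boosts lay behind the declared dose. Later para-aortic patients could be treated at that dose on pelvic data.

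Site is a reasonable factor to track here. Section 4.6 says that adding para-aortic treatment to whole-pelvis chemoradiation raises acute and late GI toxicity, depending on technique.

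**Working it through.** **The plan's own figure.** Section 11 gives a maximum of 24 patients: 6 per cohort × 4 cohorts = 24, which reproduces. There is no alpha, power or effect size to check. The MTD cohort is six patients.

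**How many para-aortic boosts a cohort may hold.** Let f be the share of patients who receive any para-aortic boost. The documents do not give f, so a range is assumed. With independent patients, the number in a cohort of n is Binomial(n, f):

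- None among the first three: (1−f)³
- None among six: (1−f)⁶
- At most one among six: (1−f)⁶ + 6f(1−f)⁵

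For f = 0.2, the last is 0.262 + 6 × 0.2 × 0.328 = 0.262 + 0.393 = 0.655.

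| Assumed f | None of 3 | None of 6 | At most 1 of 6 | Expected among 6 |
|---|---|---|---|---|
| 20% | 51% | 26% | 66% | 1.2 |
| 30% | 34% | 12% | 42% | 1.8 |
| 40% | 22% | 5% | 23% | 2.4 |
| 50% | 12.5% | 2% | 11% | 3.0 |

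These describe the patients enrolled in a cohort, before conditioning on whether it passes.

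**What that number can say about para-aortic tolerability.** With no DLT in n para-aortic-boosted patients, the exact one-sided 95% upper limit U solves (1−U)ⁿ = 0.05, so U = 1 − 0.05^(1/n):

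- n = 1: 1 − 0.05 = 95%
- n = 2: 1 − 0.224 = 78%
- n = 3: 1 − 0.368 = 63%
- n = 6: 1 − 0.607 = 39%

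So a clean six-patient cohort bounds the DLT rate at 39% if all six had a para-aortic boost. If only one did, it hardly bounds the para-aortic rate at all.

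**Whether other patients fill the gap.** Section 8.1.3 places the para-aortic chain in the elective volume for patients with involved pelvic nodes. That volume receives 45 Gy (1.8 Gy per fraction). The boost levels are 60, 65 and 70 Gy (2.4 to 2.8 Gy per fraction). Pelvic-boosted patients therefore give information on elective para-aortic irradiation, not on the escalated dose.

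**The case against.** The strongest reply is that pooling is deliberate and that the plan limits how far the sites can differ. There is one boost volume and one ladder, several gynecologic cancers are combined, and the primary objective speaks of integrated boost treatment, not of sites. Section 8.1.4 imposes the same mandatory limits on every plan, including small bowel D2cc of at most 55 Gy, below even the first boost level. Boost volumes may be cut back to meet them, and section 8.1.3 allows small bowel plus 3 mm to be subtracted. A 24-patient trial also cannot support two separate MTDs.

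Much of this stands. The common limits narrow the possible difference in bowel dose, and separate ladders are not warranted. But planning limits are not toxicity observations, and nothing here prevents the MTD from being stated for a site that was not boosted.

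A reader might go further and infer from Table 1 that para-aortic boosts are more toxic: 19% acute and 14% late grade 3-4 GI toxicity in GOG 125 without one, against 50% and 34% in RTOG 92-10 with one. The documents do not support that inference. Both trials gave extended-field chemoradiation to patients with positive para-aortic nodes, so 19% is not a pelvic-only rate. RTOG 92-10 treated twice daily, with a 3D conformal boost. The remaining row, the University of Pittsburgh IMRT series with a nodal boost, had 3% acute and 10% late. The five-patient dosimetric study in section 4.8 reached 60 Gy to nodes with bowel dose similar to conventional plans. The acute bowel DLT in section 8.1.6 also requires specified consequences, so grade 3-4 rates are not DLT rates.

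The Pittsburgh series is not proof of equal safety either: 36 patients, a boost of 55-60 Gy, median follow-up of 1.5 years, and no stated number of para-aortic boosts.

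**Conclusion.** The gap is definite; its realised size is not. The rules permit an MTD covering both sites to rest on few or no para-aortic boosts. Across assumed shares of 20% to 50%, the chance of at most one such patient in the six-patient MTD cohort runs from 66% down to 11%. It is a likely outcome at the lower shares and an unlikely one at 50%. These figures assume independent enrolment at a constant share.

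The conclusion does not depend on para-aortic boosts being more toxic. Under IMRT with these mandatory limits, higher risk is unproven. What is missing is a link between the scope of the MTD statement and the sites actually boosted.

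**What to change.** In Section 11:

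1. Tabulate acute and late DLTs within each dose level by boost site (pelvic only, or any para-aortic).
2. Report the MTD with the number of para-aortic-boosted patients in the MTD cohort and an exact one-sided 95% upper limit on their DLT rate, for acute and late DLTs separately.
3. State in advance that the MTD applies only to sites boosted in the MTD cohort, and so to pelvic nodes only if that cohort had no para-aortic boosts.

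Boost site is known from each treatment plan. Dose levels, DLT definitions, escalation rules and sample size are unchanged. The downside is that the MTD claim may be narrower than the hypothesis. Reporting the count and its limit is preferable to a small numerical threshold for the wider claim: even two para-aortic-boosted patients without a DLT leave an upper limit of 78%.
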